4.3 Screen and Baseline Failures

Data for screen and baseline failures will be collected in source documentation at the site but will not be transmitted to Novartis.

4.4 Withdrawal from Study and Missing Visits

Should a subject fail to attend the clinic for a required study visit, the site should attempt to contact the subject and re-schedule the missed visit as soon as possible. The site should also counsel the subject on the importance of maintaining the assigned visit schedule and ascertain whether or not the subject wishes to and/or should continue in the study based on previous non-compliance.

In cases where the subject does not return for the rescheduled visit or cannot be reached to reschedule the missed visit, the site should make every effort to regain contact with the subject (3 telephone calls and if necessary a certified letter to the subject's last known mailing address) so that they can appropriately be withdrawn from the study. These contact attempts should be documented in the subject's medical record.

Should the subject continue to be unreachable, then and only then will he/she be considered to have withdrawn from the study with a primary reason of "Lost to Follow-up". For all other subjects withdrawing from the study, an alternative reason for discontinuation should be recorded in the eCRF.

5 DATA ANALYSIS AND STATISTICAL CONSIDERATIONS

5.1 Hypotheses and Treatment Comparisons

With respect to the primary objectives and endpoints, the primary focus will be on determining the MTD (or recommended dose based on available safety, PK, and response data), the safety profile, and PK/PD relationship of dabrafenib in paediatric subjects with advanced BRAF V600-mutation positive solid tumors. Most analyses will be descriptive [REDACTED].

5.2 Sample Size Considerations

5.2.1 Sample Size Assumptions

5.2.1.1 Part 1 Dose Escalation

A minimum of 3 subjects will be evaluated at each dose level for determination of an appropriate pediatric dose using the modified RSD. It is estimated that approximately 6 to 18 subjects will be enrolled into Part 1.

5.2.1.2 Part 2 Cohort Expansion

The sample size for Part 2 is based on feasibility, practicality, and what would be sufficient for the characterization of the safety of dabrafenib and the plasma pharmacokinetics for the populations enrolled. Each of the 4 expansion cohorts will attempt to enroll at least 10 evaluable subjects; the HGG cohort will continue recruitment until enrollment on another pediatric HGG study is available (expected by the end of 2018 and no later than mid 2019). It is estimated that approximately 35 subjects with HGG will enroll into Part 2.

If less than 1 response is observed after 10 subjects complete the study, the treatment could be considered to have insufficient clinical activity in that cohort. The estimated sample size (n=10)

for the Part 2 expansion cohorts was further evaluated using exact binomial distribution probabilities, and the details are provided in [Table 5-1](#). For example, if zero responses are observed among 10 subjects in a cohort [if the response rate (RR)=5%], the chance of declaring the cohort as having insufficient clinical activity after 10 subjects is 60%. If the true RR=15% for dabrafenib in high grade glioma subjects, the chance declaring the cohort as having insufficient clinical activity after 10 subjects is approximately 20%.

Table 5-1 Exact Binomial Probabilities of Observing 0 and 1 (or more) Responses in 10 Subjects

True RR	Probability of Observing 0 responses in 10 Subjects	Probability of Observing ≥1 Responses in 10 Subjects
5%	0.60	0.40
10%	0.35	0.65
15%	0.20	0.80
20%	0.11	0.89
25%	0.056	0.94
30%	0.028	0.97

5.2.2 Sample Size Re-estimation

The HGG cohort in Part 2 will continue recruitment after 10 subjects are enrolled until enrollment on another study is available (expected by the end of 2018 and no later than mid 2019). The exact number of subjects recruited to the HGG cohort will depend on both the recruitment rate of subjects with HGG and the time it takes to begin recruitment to the new study. It is estimated that around 35 subjects with HGG will be recruited prior to the full opening of the new study based on the current plans, although the actual figure could be higher or lower than this. As promising efficacy has already been demonstrated with the initial subjects enrolled in this cohort, the additional increase in enrollment is to ensure that subjects can have access to a beneficial treatment, while also providing important additional refinement of the response rate estimate. For illustration, the improvement of precision in response rate estimate is shown in the Table below with the 95% exact binomial confidence intervals (CIs) at N=35 compared to the 95% CIs at N=10.

Table 5-2 Exact Binomial 95% Confidence Intervals around Potential Observed Objective Responses Rates for 10 and 35 Subjects

Observed # of Responses (Response Rate) (N=10)	Exact 95% Confidence Interval (%) (N=10)	Observed # of Responses (Response Rate) (N=35)	Exact 95% Confidence Interval (%) (N=35)
1 (10%)	0.3, 44.5	4 (11%)	3.2, 26.7
2 (20%)	2.5, 55.6	7 (20%)	8.4, 36.9
3 (30%)	6.7, 65.2	11 (31%)	16.9, 49.3
4 (40%)	12.2, 73.8	14 (40%)	23.9, 57.9
5 (50%)	18.7, 81.3	18 (51%)	34.0, 68.6
6 (60%)	26.2, 87.8	21 (60%)	42.1, 76.1

Observed # of Responses (Response Rate) (N=10)	Exact 95% Confidence Interval (%) (N=10)	Observed # of Responses (Response Rate) (N=35)	Exact 95% Confidence Interval (%) (N=35)
7 (70%)	34.8, 93.3	25 (71%)	53.7, 85.4

5.3 Data Analysis Considerations

All data will be summarized or listed. Subjects will be summarized based on the treatment level to which they were originally assigned. Additionally, selected analyses and summaries will be provided by age group as appropriate.

Complete details will be provided in the Statistical and Analysis Plan (SAP).

5.3.1 Analysis Populations

Populations will be considered for the analysis as follows:

The **‘All Treated’** population is defined as all subjects who receive at least 1 dose of study treatment. An incorrect treatment schedule or drug administration or an early termination of treatment will not result in exclusion of subjects from this population.

The **‘Safety’** population consists of all subjects who receive at least 1 dose of study treatment. All safety data will be analyzed using the Safety population.

The **‘DLT Evaluable’** population is defined as those subjects in Part 1 fulfilling the ‘All Treated’ population criteria, and having received an adequate treatment for the first 28 days to enable an appropriate evaluation of study drug related DLTs. Adequate exposure during the first 28 days will be defined as having received >75% of planned study drug doses, exclusive of missed doses due to treatment-related toxicity. Any subject in the ‘All Treated’ population who experiences a DLT, as defined in [Section 3.3](#), will also be included in the DLT evaluable population regardless of exposure.

The **‘PK Population’** is defined as those subjects fulfilling the All Treated population criteria who contribute PK samples.

5.3.2 Interim Analysis

Safety and PK data will be examined while the study is being conducted for dose escalation decisions.

At the time of Amendment 7, an unplanned interim analysis was performed after all subjects with LGG had enrolled in Part 2 and completed at least 6 months of treatment or had discontinued treatment earlier. The interim analysis included analysis of all Part 1 subjects and other disease cohorts from Part 2 were analyzed as appropriate. This interim analysis was used for decision making of future development options and for publications. No statistical hypothesis testing was planned or conducted.

An interim analysis is planned after all subjects with LCH have enrolled in Part 2 and have completed at least 1 year of treatment or have discontinued treatment earlier. The results will be used for decision making of future development options and may be used for publications. At this time, no statistical hypothesis testing is planned, and no decision regarding the conduct

of this study will be made. The data for all Part 1 and Part 2 subjects may also be analyzed at this interim. In addition, safety and tolerability will be monitored closely on a continued basis.

Additional interim analyses may be performed to support any health authority requests as and when needed. No efficacy or futility conclusions will be drawn based on these interim analyses.

5.3.3 Final Analyses

5.3.3.1 Safety and Tolerability Analyses

All relevant safety data will be summarized or listed based on the Safety population.

All safety data will be reported according to the initial treatment regimen the subject received (initial dose of dabrafenib). Additionally, selected analyses and summaries will be provided by age group as appropriate. AEs will be summarized by maximum toxicity grade for each initial dose level of dabrafenib. The toxicity grade for laboratory data will be calculated using NCI CTCAEv4.0 or higher (NCI, 2009). The lab data will then be summarized according to the subjects' baseline grade and maximum grade for each cycle of therapy (done for each initial dose level of dabrafenib).

DLTs will be summarized.

5.3.3.1.1 Extent of Exposure

Extent of exposure of dabrafenib will depend on tolerability of the subjects to the doses administered and the course of their disease. The number of subjects exposed to dabrafenib will be summarized for each dose level administered.

5.3.3.1.2 Adverse Events

AEs will be coded and grouped by body system. AEs will be summarized by frequency and proportion of total subjects, event type and body system. Separate summaries will be given for all AEs, drug-related AEs, SAEs, and AEs leading to withdrawal from the study.

Adverse events (AEs) and toxicities will be graded according to the NCI-CTCAE, Version 4.0. Summaries of the number of toxicity grades for both laboratory and non-laboratory data will be presented. If the AE is listed in the NCI-CTCAE, Version 4.0, the maximum grade will be summarized. Otherwise, the maximum intensity will be summarized.

5.3.3.1.3 Clinical Laboratory Evaluations

Hematology and clinical chemistry data will be summarized at each scheduled assessment according to NCI CTCAE grade (version 4.0). For laboratory tests where grades are not defined by CTCAE v4.0, results will be categorized as low/normal/high based on laboratory normal ranges. Summaries will include data from scheduled assessments only, and all data will be reported according to the nominal visit date for which it was recorded; no visit windows will be applied. Unscheduled data will be included in "post-baseline" summaries which will capture a worst case across all scheduled and unscheduled visits after the first dose of study medication. Further details will be provided in the SAP.

5.3.3.1.4 Other Safety Measures

Performance status (Karnofsky/Lansky) assessments will be summarized by the originally assigned dose level. Vital signs, ECG, and ECHOs will be summarized at all measured time points. A descriptive summary including change from baseline pre-dose will also be presented. Further details will be provided in the SAP.

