2 OBJECTIVES AND ENDPOINTS

Objectives	Endpoints
Primary	

 To determine the safe and tolerable dabrafenib dose(s) for chronic dosing in pediatric subjects (infants, children, and adolescents) that achieves similar exposures to the dabrafenib adult dose, in subjects with BRAF V600 mutation positive tumors 	
 Adverse Events (AEs); ECG; ECHO; changes in laboratory values and vital signs in Part 1 and Part 2. C_{max}, area under the concentration-time curve from time zero (pre-dose) to last time of quantifiable concentration [AUC(0-τ) and AUC(0-inf) of dabrafenib
Secondary	

 To characterize the pharmacokinetics of dabrafenib, and its metabolites 	
 C_τ (trough), AUC(0-t), AUC(0-τ), apparent clearance following oral dosing (CL/F) (dabrafenib only), C_{max}, t_{max} and t_{1/2} of dabrafenib and its metabolites, as appropriate

 To characterize the longer term safety and tolerability of dabrafenib 	
 AEs; ECG; changes in laboratory values and vital signs

 To assess any preliminary anti-tumor activity of dabrafenib 	
 Tumor response as defined in Appendix 2 by investigator assessment

 To determine the effect of age and weight on the pharmacokinetics of dabrafenib using a population pharmacokinetics approach 	
 CL/F, volume of distribution (V/F), absorption rate (k_a), and coefficients for significant covariates
Exploratory	

 To determine the palatability of dabrafenib in pediatric subjects 	
 Palatability questionnaire data

[figure not shown]

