Dermatologic skin assessment	Performed by the investigator (or dermatologist, at the discretion of the investigator). If possible, the same physician should perform each exam for the duration of the study to ensure consistency between evaluations. Photographs of suspect lesions at baseline are recommended with photographs and/or biopsies of any new or changing lesions recommended at subsequent on-study visits.	X		X	X	X
Vital signs	Blood pressure, body temperature, pulse rate, respirations	X	X	X	X	X
ECG	Two copies of the ECG tracing should be obtained at the time of the ECG, one to be kept in the study file for retrospective collection by the sponsor if necessary. ECG data should be reviewed by personnel with experience in this study population (e.g., pediatric cardiologist).	X		X	X	X
Echocardiogram (ECHO)	Copies of all ECHOs will be collected for possible central review. Cardiology consultations performed on subjects who experience a >10% decrease in LVEF from baseline and whose cardiac ejection fraction is less than the institution's LLN will be collected for possible central review (additional details are provided in the SPM).	X			X	
Concomitant medications	See Section 8 for list of prohibited and cautionary medications.	X	X	X	X	X
Adverse events	Adverse event assessment should be continuous	X	X	X	X	X

STUDY PHASE		SCREEN	TREATMENT DAYS 1 through 21			
			Pre-dose Day 1	Pre-dose Day 8	Pre-dose Day 15	Pre-dose Day 22
VISIT		Screen				
VISIT WINDOW (\pm days)		-21	N/A	± 2	± 2	± 2
Palatability questionnaire	For suspension - see SPM for additional details; subjects ≥ 12 years of age may complete the questionnaire independently (if able) while subjects younger than 12 years of age should work with their caregiver to supply feedback and the caregiver then completes the questionnaire. The questionnaire may be completed after the first dose of study drug but must be completed no later than Day 8 (± 3 days)			X		
Blood Sampling						
Chemistry	Evaluations performed by a local laboratory. No need to repeat at pre-dose Day 1 if screening assessments were performed within 14 days of first dose.	X	X	X	X	X
Hematology	Evaluations performed by a local laboratory. No need to repeat at pre-dose Day 1 if screening assessments were performed within 14 days of first dose.	X	X	X	X	X
Urinalysis		X	X	X	X	X
Spot urine protein/Cr ratio, spot urine albumin	Early morning specimen preferred	X	X	X	X	X
PK sampling	For details, see Table 3-8		X (see Table 3-8)		X (see Table 3-8)	

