Plasma concentrations of dabrafenib and all metabolites (hydroxy-dabrafenib, desmethyl-dabrafenib, and carboxy-dabrafenib) will be measured in the 2 mL blood samples. Plasma concentrations of dabrafenib, hydroxy-dabrafenib and desmethyl-dabrafenib will be measured in 1 mL blood samples. Carboxy-dabrafenib will not be measured in the 1 mL blood sample.

^a Subjects who are approved for intra-subject dose escalation must provide PK samples on day 15 at the higher dose level.

Table 3-9 Part 1 and Part 2 Treatment Phase: Week 4 (Day 29) through End of Study

STUDY PHASE		TREATMENT WEEK 4+								
Visit		Week 4	Week 8	Week 12	Week 16	Week 20	Week 24	Weeks 28+	Weeks 48+	Final Visit ²
VISIT WINDOW (\pm days)		± 3	± 3	± 7	± 7	± 7	± 7	± 7	± 7	
Safety Assessments										
Brief Physical examination	Will include assessments of the skin, lungs, cardiovascular system, and abdomen (liver and spleen) [and neurological exam as clinically indicated]	X	X	X		X	X	Week 32 then every 8 weeks	Week 48 then every 12 weeks	X
Urine or Serum Pregnancy test	For menstruating females and as required per local applicable regulations	X	X	X	X	X	X	Every 4 weeks	Every 4 weeks	X
Vital signs	Blood pressure, body temperature, pulse rate, respirations, height, weight	X	X	X	X	X	X	Every 4 weeks	Week 48 then every 12 weeks	X
Dermatologic skin assessment	Performed by the investigator (or dermatologist, at the discretion of the investigator). If possible, the same physician should perform each exam for the duration of the study to ensure consistency between evaluations. Photographs of suspect lesions at baseline are recommended with photographs and/or biopsies of any new or changing lesions recommended at subsequent on-study visits. Monitoring of the skin can be performed by a qualified local physician at the discretion of the investigator during non-clinic visits or dermatologic assessment only visits after Week 48. If possible, the same local physician should perform each exam throughout the study to ensure consistency between evaluations.		X		X		X	Week 32 then every 8 weeks	Week 48 then every 8 weeks	X

STUDY PHASE		TREATMENT WEEK 4+								Final Visit ²
		Week 4	Week 8	Week 12	Week 16	Week 20	Week 24	Weeks 28+	Weeks 48+	
Visit		±3	±3	±7	±7	±7	±7	±7	±7	
VISIT WINDOW (±days)		±3	±3	±7	±7	±7	±7	±7	±7	

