6.3 Safety and Tolerability

Planned time points for all safety assessments are listed in the Time and Events Table ([Section 3.8](#)).

Physical and Dermatological Examinations

- A complete physical examination will include assessments of the head, eyes, ears, nose, throat, skin, thyroid, neurological, lungs, cardiovascular, abdomen (liver and spleen), lymph nodes and extremities
- Height and weight will also be measured and recorded.
- A brief physical examination will include height and weight, assessments of the skin, lungs, cardiovascular system, and abdomen (liver and spleen) [and neurological exam as clinically indicated].

Dermatological Examination/Skin Biopsy/Photography

- A full body dermatological examination will be performed by a dermatologist [or suitably qualified personnel (i.e., physician or supervised physician assistant)] to identify abnormal skin lesions. All findings will be identified during screening (photography of suspect lesions at screening is recommended). Dermatological examinations should include examination of skin and assessment of any skin changes. Wherever possible, the same personnel should perform these examinations. Follow-up skin examinations by a referral dermatologist should be conducted if clinically indicated.
- Skin photography of new non-melanoma skin lesions or non-melanoma lesions that change while on study is recommended. Refer to the SPM for details regarding the lesion documentation by photography.
- Biopsy in or around skin lesions that change during the study may be requested by Novartis, if clinically indicated. [REDACTED]
- Dermatological examinations should be performed every 2 months during treatment, and every 2-3 months for 6 months following discontinuation of dabrafenib or until initiation of another anti-neoplastic therapy, whichever comes first. Monitoring of the skin can be performed by a qualified local physician at the discretion of the investigator during non-clinic visits or dermatologic assessment only visits. If possible, the same local physician should perform each exam throughout the study to ensure consistency between evaluations. Subjects should be instructed to immediately inform their physician if new lesions develop. Any cuSCC or new primary melanoma should be reported as a protocol-specific SAE and treated according to standard clinical practice.

Non-cutaneous secondary/recurrent malignancy

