- During treatment subjects should be monitored as clinically appropriate. Complete blood cell counts should be performed as clinically indicated. Following discontinuation of dabrafenib monitoring for non-cutaneous secondary/recurrent malignancies should continue for up to 6 months or until initiation of another anti-neoplastic therapy, whichever comes first. Any non-cutaneous secondary/recurrent malignancy should be reported as a protocol-specific SAE and treated according to standard clinical practice.
- See [Appendix 6](#) for French country specific guidelines.

Vital Signs

- Vital sign measurements will include systolic and diastolic blood pressure, temperature and pulse rate.
- If a subject develops a fever, refer to Section 3.7.1 for management guidelines.

Electrocardiogram (ECG)

- A single 12-lead ECG will be obtained at each time point during the study using an ECG machine that automatically calculates the heart rate and measures PR, QRS, QT, and

QTcB intervals. Refer to [Section 3.7.4.4](#) for QTcB withdrawal criteria and additional QTcB readings that may be necessary.

Echocardiography (ECHO)

- ECHOs will be performed to assess cardiac ejection fraction. The echocardiographer's evaluation should include an evaluation of left ventricular ejection fraction. Post-dose ECHOs should be compared to baseline to note if there are any changes.
- Copies of all ECHOs and cardiology consultations performed on subjects who experience a >10% absolute decrease in LVEF from baseline and whose cardiac ejection fraction is less than institution's LLN will be required by Novartis for review.

Clinical Laboratory Assessments

Hematology, clinical chemistry and additional parameters to be tested are listed below:

Hematology			
Platelet Count:	Red blood cell (RBC) Indices (at screening and if hemoglobin decrease ≥ 2 g/dL compared to baseline):		Automated White Blood Cell (WBC) Differential:
RBC Count	MCV		Neutrophils
WBC Count (absolute)	MCH		Lymphocytes
Hemoglobin	MCHC		Monocytes
	Reticulocyte Count		Eosinophils
			Basophils
Clinical Chemistry			
BUN	Potassium	AST	Total and direct bilirubin ^a
Creatinine	Chloride	ALT	Uric Acid
Glucose	Total CO ₂	Alkaline phosphatase	Albumin
Sodium	Calcium		Total Protein
Magnesium	Phosphate		
Other tests			
Pregnancy tests			
Amylase and lipase [monitor via local laboratory where appropriate to evaluate certain AEs (i.e., abdominal pain, pancreatitis, etc.)]			

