2.8.5.2 Vital signs

[figure not shown]
Refer to study GSK SAP.

[figure not shown]

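### The available plan gives height and weight in growing children only a change-from-baseline summary, with no age and sex reference, and that summary alone cannot show slowed height growth

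*Protocol*

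**What the plan says.** One secondary objective in protocol Section 2 is "To characterize the longer term safety and tolerability of dabrafenib", and changes in vital signs are among its endpoints. They also appear among the primary safety endpoints.

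Section 5.3.3.1.4 gives the analysis: "Vital signs, ECG, and ECHOs will be summarized at all measured time points", followed by "A descriptive summary including change from baseline pre-dose will also be presented". It leaves further detail to the SAP. SAP Section 2.8.5.2 (Vital signs) says "Refer to study GSK SAP" and adds nothing. The SAP introduction explains that the document covers only changes and additions to earlier plans.

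The protocol is not consistent on whether height and weight are vital signs:

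- Table 3-9 (Week 4 onward), vital-signs row: "Blood pressure, body temperature, pulse rate, respirations, height, weight".
- Table 3-7 (screening to Day 22), vital-signs row: "Blood pressure, body temperature, pulse rate, respirations". Height and weight have a separate row there, for screening and Day 1.
- Section 6.3, under vital signs: "Vital sign measurements will include systolic and diastolic blood pressure, temperature and pulse rate".
- Section 6.3, under physical examinations: "Height and weight will also be measured and recorded".

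Sections 5.3 and 5.3.3.1 allow selected summaries by age group where appropriate. Section 9.4 includes growth and sexual maturation in the visits offered after treatment ends, with no analysis described.

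**The concern.** Height in children rises with age whether or not a drug slows it. A mean change from baseline in centimetres therefore needs an expected value beside it. A randomised trial gets that from its control arm. This trial has one arm, so it would have to come from an external growth reference, and none is named.

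What is at stake is the reading of the long-term safety tables. A column of positive height changes could be taken as evidence that growth is unaffected when it is equally compatible with slowed growth. The question is relevant here because the study rationale (Section 1.2.1) contrasts dabrafenib with treatments that harm children's growth and development. Laboratory data, by comparison, are judged against CTCAE grades or normal ranges (Section 5.3.3.1.3).

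**Working it through.** The plan states no growth figure, so there is nothing to reproduce. The check has three parts.

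**1. Length of treatment.** Amendment 10 reports 85 subjects treated by 06-Feb-2019. Amendment 11 reports 85 treated and 52 off treatment at 17-Jul-2020, which leaves 85 − 52 = 33. The figure 52 is the same in both amendments, so 33 is approximate. Anyone still on treatment at 17-Jul-2020 had more than 17 months since first dose. The Part 2 LGG and LCH subjects (17 and 11) were all enrolled by 04-May-2017, so any still on treatment had more than 3 years. Growth over such periods is not negligible.

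**2. Sign of the height change.** Let v be normal growth velocity, f the fraction of growth lost and t the years on treatment.

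- Observed change = v × (1 − f) × t
- Hidden deficit = v × f × t

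Whenever v > 0 and f < 1, the observed change is positive. The values below are assumptions, not document figures: v = 6 cm/year, f = 50%, and a height SD for age of 4 to 7 cm.

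| t | Observed change | Hidden deficit | Deficit in SD units (÷7 to ÷4) |
|---|---|---|---|
| 6 months | 6 × 0.5 × 0.5 = +1.5 cm | 1.5 cm | 0.21 to 0.38 |
| 1 year | 6 × 0.5 × 1 = +3.0 cm | 3.0 cm | 0.43 to 0.75 |
| 2 years | 6 × 0.5 × 2 = +6.0 cm | 6.0 cm | 0.86 to 1.50 |

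With v from 1 to 10 cm/year and f from 25% to 75%, the one-year change runs from 1 × 0.25 = +0.25 cm to 10 × 0.75 = +7.5 cm and is never negative. The deficit runs from 1 × 0.25 = 0.25 cm to 10 × 0.75 = 7.5 cm.

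Nor does the size of the change separate the cases. An observed +3.0 cm at one year fits v = 6 with half of growth lost, v = 4 with a quarter lost (4 × 0.75), or v = 3 with none lost.

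Two limits follow from the same formula. With v = 0 (growth complete), the change is 0 with or without a drug effect. Weight is not bound by the formula because it can fall below baseline.

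**3. Which summary applies.** If Table 3-9 governs, post-baseline height and weight fall under the change-from-baseline summary. If Section 6.3 governs, they are outside vital signs and the available text states no post-baseline analysis of them. Neither reading supplies a growth reference.

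**The case against.** The strongest objection is that the governing text is missing. Section 5.3.3.1.4 does not use the word raw, it defers to the SAP, and the SAP lists only changes to an earlier plan that still applies. A reader might infer that the trial definitely analyses height without age adjustment. The documents do not establish that, because the earlier SAP may contain such an analysis. This stands and limits the finding to what the available text specifies. SAP Section 4 reports no departure from the protocol's analyses apart from partly redacted exceptions, but that does not settle it.

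A reader might also infer that any drug effect on growth would look like a gain. That fails for adolescents who have finished growing and for weight. The argument relies on height moving in one direction only, so it does not carry over to blood pressure or pulse.

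Nor do the documents support a reading that growth is looked for only after treatment stops. Height and weight are measured throughout treatment, and a clinically significant finding can be reported as an adverse event (Section 11.1). That route depends on individual judgement and does not replace a summary of the measurements.

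Age-group summaries help only in part. They are optional, the SAP has no formal subgroup plans (Section 2.2.6), and its one stated age split, under 12 against 12 and over, is for dose intensity (Section 2.4). Bands that wide do not standardise growth.

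Finally, growth is not a named endpoint, and a z-score would not identify a cause. Nearly all subjects have had earlier therapy, Section 1.2.1 itself notes radiotherapy's effects on skeletal growth and endocrine function, and corticosteroids are used for pyrexia (Table 3-4). That stands as a limit on interpretation. It does not make a centimetre change more informative.

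**Conclusion.** The point holds for the available protocol and SAP. They state only a descriptive summary with change from baseline, name no growth reference, and leave unclear whether that summary covers height and weight. For height in growing children, it cannot on its own distinguish normal from slowed growth. The illustrated deficit of 0.43 to 0.75 SD at one year rests wholly on the assumed velocity, loss and SD. The sign argument needs only that the child is growing and that the loss is partial.

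This is a worthwhile improvement to descriptive safety reporting. It does not affect dose selection, pharmacokinetics or response rates, and it is no evidence that dabrafenib slows growth. If the earlier SAP already has standardised growth scores, what remains is a missing citation and the inconsistency over vital signs.

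**What to change.** 1. Check the earlier SAP. If it already specifies age- and sex-standardised height and weight, cite the section in SAP 2.8.5.2.
2. If it does not, state in protocol 5.3.3.1.4 and SAP 2.8.5.2 that on-treatment height, weight and BMI are summarised as age- and sex-standardised z-scores against a named growth reference. Give change in z-score by visit and the number of subjects whose z-score change falls below a prespecified value. The documents offer no basis for that value, so the sponsor should set and justify it. Keep raw values in listings.
3. Reconcile Table 3-9 with Table 3-7 and Section 6.3 on whether height and weight are vital signs.
4. State with the results that they describe growth and cannot be attributed to the drug alone, given prior therapy and corticosteroid use.

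The cost is some programming and the choice of reference. Date of birth, gender, height and weight are already collected (Section 6.1, Tables 3-7 and 3-9), so no new data or visits are needed.
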